15.2 N/A

15.3 N/A

15.4 N/A

16.0 Potential Benefits to Subjects*

16.1 Benefits

Healthy control: None.

Placebo: increasing functional capacity and cardiovascular health outcomes.

Creatine: increasing muscle blood flow, increasing functional physical capacity and cardiovascular health outcomes.

Static muscle stretching has been shown to improve muscle blood flow. We believe that combining creatine supplementation with muscle stretching will enhance the efficacy of the treatment protocol, further enhancing cardiovascular function.

17.0 Data Management* and Confidentiality

17.1 *Statistical analysis will include repeated measures ANOVA with Bonferroni post hoc analysis and paired samples t-test when applicable. Due to the nature of the current investigation (pilot study) we will be running a power analysis once the data set is collected.*

17.2 During this study, and after consent is obtained, medical history questionnaires will be filled out prior to the start of the study. Experimental measurements will be obtained for statistical analyses and for research purposes only, and data will be kept in strict confidence. No information will be given to anyone without written permission from the subject. Data will be entered into REDCap and stored in a HIPAA compliant environment. Confidentiality will be ensured by use of identification codes. All data, whether generated in the laboratory or in post-processing will be identified with an identification code unique to the subject. The master identification code list will be kept under lock and key access limited to the P.I. and necessary members of the study team. Any presentation or publication of the data will be done in cumulative fashion without identifiers.

17.3 *Our protocols include standard operating procedures for calibration of instrumentation and all data collection.*

17.4 *Describe how data or specimens will be handled study-wide:*

- *All data collected on paper will be identified only by subject ID. Paper forms will be entered and/or uploaded into REDCap database which only the research team will have access to. Subject contact information will be necessary, but this information will be stored separately with limited access to the study team members who must contact the subjects for AE tracking and appointment reminders.*

PROTOCOL TITLE: Creatine supplementation and muscle stretching in peripheral artery disease patients

- Individual participant paper files will be stored in a locked cabinet in a locked office only accessible to the research team. Any data extracted from the REDCap database will be secured with password protection. Electronic communication between investigators will only involve anonymous information.

All data forms and study specific information will be kept in a locked file cabinet and in a password protected capable computer database with access limited to only the P.I. and key personal of the research team. Confidentiality will be protected by utilizing a code number as the only identifier for each subject.

The PI or study staff will review all data collection forms on an ongoing basis for data completeness and accuracy as well as protocol compliance. A check list will be used to verify compliance. The frequency of data review for this study differs according to the type of data and can be summarized as follows:

Data Type: Subject accrual (including compliance with protocol enrollment criteria); Frequency: Weekly; Reviewer: PI

Data Type: Status of all enrolled subjects, as of date of reporting; Frequency: Weekly; Reviewer: PI

Data Type: Adverse Events* and rates (including out-of-range lab values); Frequency: Weekly; Reviewer: PI

Data Type: Serious adverse events**; Frequency: Per occurrence; Reviewer: PI *An adverse event (AE) is any untoward medical occurrence in a subject during participation in the study or with use of the experimental agent being studied.

Upon completion of the study, the data will completely de-identified so that it may be kept indefinitely. Once publications have been approved we will transfer all paper data into the FSU online system that is password protected.

All study records must be kept in compliance with FDA regulations.

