6.0 Procedures Involved*

- 6.1 All patients (PAD or healthy volunteers) will undergo 4 weeks of splint stretching (30min/day; 5days/week – procedures attached with this submission) and be randomized into groups with or without creatine supplementation (10g/day for the first 5 days and 5g/day for the remainder). Placebo supplementation (Fiber powder; cellulose) will be given during the opposite arm of the study and according to section 6.2 (below).
- 6.2 Each potential patient/participant will be screened to determine potential eligibility by the research team. If the individual is eligible, see inclusion/exclusion criteria, they will be asked to consider joining the study. Individuals meeting the initial criteria and who agree to participate in the study will sign informed consent and complete any medical history forms. All participants must abstain from alcohol for 24 hours and caffeine/food for ~ 4 h prior to testing sessions. The current investigation is a randomized single-blind study design.
 - C1. Health and exercise questionnaires: Subjects' medical history and exercise habits will be

PROTOCOL TITLE: Creatine supplementation and muscle stretching in peripheral artery disease patients

assessed by self-reported health and exercise questionnaires: demographics and health history (Visit 1), physical activity readiness (Visit 1), health survey-SF36 (Visit 2 and 3), international physical activity questionnaire (I-PAQ, Visit 2 and 3), walking impairment questionnaire (WIQ, Visit 2 and 3).

- C2. Fitbit: Subjects will be given a Fitbit Charge 2 (Fitbit, San Francisco, California) to wear for a 1 week period starting at Visit 1 and Visit 3 to measure daily step count before and after the intervention. At this time, we anticipate 4-8 subjects with PAD using a Fitbit during the course of the study. We will recruit 2-4 PAD patients to serve as time controls and not partake in the intervention.
- C3. 'Anthropometric measurements and vitals will consist of subject height measured on a stadiometer and weight measured on a calibrated scale, heart rate (resting) and baseline blood pressure after 10-min of quite supine rest. Next, we will measure circumference of the waist and lower leg and range of motion of the knee and ankle. All of these measurements will be done at Visit 2. *Resting heart rate and blood pressure will be repeated at Visit 3.*

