12.0 Local Number of Subjects

12.1 *The goal of this study is to enroll 20 individuals with PAD and 20 healthy volunteers. To account for screenfails and withdrawals, we will enroll up to 50 subjects in this study.*

12.2 *N/A*

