Cover Page

Study Title: Creatine Use and Muscle Stretching in Peripheral Artery Disease

NCT Number: NCT04471792

Date of Statistical Analysis Plan: 04-02-2022

Statistical Analysis Plan to follow

PAD- Stretching +Creatine Statistical Analysis

The primary goal of this study is to determine the effects of splint-based passive muscle stretching with and without creatine monohydrate supplementation protocol on changes in microvascular function, walking performance, and subjective measures of walking performance in PAD patients. Based on data from Moraes et al. [129] who reported a 10% increase in post-occlusive reactive hyperemia in participants taking creatine (effect size: 0.78, mean 1: 0.54, mean 2: 0.49, pooled SD 0.02), a sample size of 9 participants per group was needed to detect changes in microvascular reperfusion variables with 80% power and an α of 0.05. Descriptive statistics were calculated for all variables and included means and standard deviations for normally distributed continuous variables and medians, minima and maxima for non-normally distributed continuous variables. Independent t-tests were used to determine if there were differences in baseline variables between groups. If baseline values between groups were significantly different, a secondary analysis was conducted using an analysis of covariance with baseline values as covariates. If sphericity was violated ($\varepsilon < 1$), a Greenhouse-Geisser correction was used. Changes in dependent variables over time were analyzed using repeated measures ANOVA (group by time). When interactions were significant, independent and paired t-tests were used to determine where differences were located. If there were no differences in measured variables between creatine and placebo supplementation, data were pooled, and paired t-tests were used to evaluate pre to post differences in the measured variables of microvascular function, walking performance, and subjective measures of walking performance. Pearson Product Moment Correlations were completed on baseline variables to look at relationships between microvascular function, walking performance, and subjective measures of walking performance. All significance was accepted at $p < 0.05$. Statistical outliers were removed if they exceeded 2 standard deviations from the baseline mean or mean changes from pre to post-intervention. All analyses were performed using the SPSS 27 statistical package.

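### Protocol section 17.1 defers the power analysis until after data collection without saying which effect size it will use or what it is for, and this is not reconciled with the SAP's 9 per group

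*Protocol*

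**What the plan says.** Protocol section 17.1 contains the protocol's only statement on power. Giving pilot status as the reason, it says "we will be running a power analysis once the data set is collected". It does not say whether the effect entered will be the observed one or one fixed in advance, which outcome it concerns, or whether the result is meant to interpret this trial or to plan another.

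Section 12.1 sets the numbers without a power basis: "The goal of this study is to enroll 20 individuals with PAD and 20 healthy volunteers", and "To account for screenfails and withdrawals, we will enroll up to 50 subjects in this study". Section 6.1 says participants will "be randomized into groups with or without creatine supplementation" and gives no allocation ratio.

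The SAP, dated 04-02-2022 and written in the past tense, takes a different line. From an external creatine study (stated effect size 0.78, means 0.54 and 0.49, pooled SD 0.02) it concludes that "a sample size of 9 participants per group was needed to detect changes in microvascular reperfusion variables" "with 80% power and an α of 0.05". Its list of analyses includes no power analysis after the data. If creatine and placebo do not differ, it pools the arms and runs paired t-tests on the pre-post change. Neither document commits to a confidence interval for the creatine-minus-placebo difference.

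**The concern.** A power analysis run after the data can mean two quite different things, and section 17.1 leaves both open.

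One is power at the observed effect, placed beside this trial's result. That figure carries no information beyond the p-value, and it is low whenever the result is not significant, whatever the truth about creatine. A reader could take it as a sign that more patients would have shown a benefit.

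The other is sizing a later trial. If the effect estimated in about 18 patients is fed into that calculation, the answer is largely noise.

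There is also a gap between the documents. The protocol reads as if the sample size had no power basis; the SAP presents 9 per group as a requirement. A reader cannot tell whether 9 was a design input or a justification added later.

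**Working it through.** **Inputs.** From the SAP: 9 per group, 80% power, alpha 0.05, effect size 0.78, means 0.54 and 0.49, SD 0.02. Assumed because the documents do not say: 1:1 allocation, a two-sided test, and a two-sample t-test with df = 2n − 2.

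**1. Can the SAP's own figure be reproduced?**

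- Its printed means and SD give (0.54 − 0.49)/0.02 = 2.5, not 0.78. An effect of 0.78 from the same means would need an SD of 0.05/0.78 = 0.064.
- Normal approximation: n per group = 2(1.960 + 0.842)²/0.78² = 25.8, so 26.
- Exact noncentral t with noncentrality d√(n/2): 27 per group (power 80.3%). One-sided: 22.
- Power at d = 0.78: 34% with 9 per group and 38% with 10 per group.
- With d = 2.5, 4 per group would be enough two-sided.
- A paired calculation at d = 0.78 gives 15 two-sided or 12 one-sided.
- The one route found to 9 is a group-by-time interaction calculation with f = 0.39 (half of 0.78) and a pre-post correlation of 0.40 to 0.45, which the SAP does not state. That f corresponds to a difference in change of 1.56 SD. The matching f of 0.195 gives 27 per group at correlation 0.5.
- If 0.78 is in raw SD units and change scores are compared, d = 0.78/√(2(1 − r)). Over r = 0 to 0.8, power with 9 per group runs from 20% to 69%, below 80% throughout.

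**2. Power at the observed effect, 9 per group.** Convert p to the observed t on 16 df, set the observed d = t√(2/9), and compute noncentral-t power at that d.

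| p | t | observed d | observed power |
|---|---|---|---|
| 0.05 | 2.120 | 1.00 | 51% |
| 0.10 | 1.746 | 0.82 | 38% |
| 0.20 | 1.337 | 0.63 | 24% |
| 0.50 | 0.690 | 0.33 | 10% |
| 0.80 | 0.258 | 0.12 | 6% |

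With n fixed, p is the only input, so the power column only restates the p column. With 10 per group (the 20 PAD patients of section 12.1 split equally) the values are almost the same: 51%, 38%, 24%, 10% and 6%.

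**3. Pilot effect as a planning input.** Suppose the true d is 0.78 with 9 per arm. The observed t is then noncentral t on 16 df with noncentrality 0.78√(9/2) = 1.655. Its 10th and 90th percentiles, multiplied by √(2/9), are d = 0.18 (0.177 before rounding) and 1.49. For 80% power two-sided these imply about 500 and 9 per arm. The planned size would vary more than fiftyfold between two unremarkable pilot results.

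**The case against.** The strongest reply is that section 17.1 never says the observed effect will be used. Its stated reason, that this is a pilot, fits at least as well with using pilot data to size a later trial. A reader might infer that the planned analysis can only restate the p-value; the text does not support that unconditionally, and the arithmetic in step 2 applies only if the observed effect is entered.

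A reader might also infer that the investigators mean to explain away a null creatine result as underpowered. Nothing says so. The SAP's documented response to no difference is to pool the arms, and power after the data is not among its analyses.

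Nor do the documents strictly contradict each other. A literature-based requirement and a later power analysis can coexist. The SAP is dated after the summer 2021 primary analysis expected in protocol section 9.3, and it could be read as superseding 17.1.

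These limits all stand. They do not remove the point: effect size, outcome and purpose are all unspecified, and the calculation is unhelpful if based on the observed effect under either purpose. The SAP does not fill the gap, because its stated inputs do not lead to 9 per group. The follow-on range in step 3 concerns a hypothetical later trial and measures no error in this one.

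**Conclusion.** The point holds in a conditional form. Section 17.1 promises a power analysis after data collection with no stated effect size or purpose, and this is left unreconciled with the SAP. If the observed effect is entered, any non-significant creatine comparison will show about 51% power or less regardless of the truth. If the pilot effect is used for planning, the implied size runs from about 500 down to 9 per arm when the true effect is 0.78 SD.

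It matters here because, taking 0.78 at face value, 9 per group gives only about 34% power. A non-significant comparison is therefore the likelier outcome even if that effect is real, and how it is then described becomes important. An interval would show which creatine effects the data exclude; observed power would not.

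The figures rest on 1:1 allocation, a two-sided two-sample t-test and 9 per group. The observed-power values hardly change at 10 per group. This affects interpretation and reporting; it does not make the trial invalid.

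**What to change.** - **Replace the power sentence in section 17.1**, and repeat the replacement in the SAP: report the creatine-minus-placebo difference in change with a 95% confidence interval, and compute no power from observed effects.
- **If a later power analysis is kept**, say that it is for a future trial. Base it on the pilot SD and pre-post correlation, each with its uncertainty, and on a target difference justified separately.
- **State one basis for the sample size in both documents**: either feasibility, or one calculation that can be reproduced, with its test, sidedness and any assumed correlation. Do not carry the SAP's 9 per group into 17.1 as it stands, since its inputs disagree (2.5 against 0.78).

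The cost is about a sentence or two in each document. No new data are needed, and the interval can be added at reporting even if analysis has begun.

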18.0 Provisions to Monitor the Data to Ensure the Safety of Subjects*

- We will not use data to monitor safety of subjects/patients. We are doing this by talking with the patients and subjects weekly.

19.0 Provisions to Protect the Privacy Interests of Subjects

19.1 Only the PI and the research team will have full access to patient records. All data will be deidentified when post processing. *This*

PROTOCOL TITLE: Creatine supplementation and muscle stretching in peripheral artery disease patients

investigation is not to be kept in secret. All patients may talk about the study and study components to whomever they choose.

- 19.2 *We will be sure to inform the patients that this study is totally voluntary, and they are not required to answer anything they feel is uncomfortable or they do not want to answer.*
- 19.3 *We will let the patients know their data will be coded and locked away with a similar level of security as a doctor's office. Besides the PI and research team, no other lab help will have sensitive information (i.e., health history) or any information to link the data back to the subject.*

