- C4. 'Muscle oxygenation characteristics' of the lower leg (i.e., gastrocnemius and soleus) will be measured via near-infrared spectroscopy (NIRS) (Moxy monitoring systems, Hutchinson, Minnesota) at Visit 2 and 3. NIRS is a completely noninvasive measure that uses infrared light waves emitted from a skin surface probe. NIRS measurements will be made continuously during the entirety of the experimental protocol. Protocol one will utilize a blood pressure cuff around the knee joint and inflated to ~250mmHg to occlude flow for 5-minutes. At minute 5 the cuff is instantaneously released and rest will continue for ~5-minutes. The NIRS will be take off for C3.A and then put back on in place to complete C4 (see below).
- C5.A 'Muscle blood flow and metabolic kinetics" (i.e., gastrocnemius and soleus) will be measured in the 3T MRI system (Visit 2 and Visit 3; limited subjects). All patients and controls will be placed in the MRI feet first and undergo each trial by placing a blood pressure cuff just proximal to the knee joint and inflating it to ~250mmHg to occlude flow for 5-minutes. At minute 5 the cuff is instantaneously released and rest will continue for ~5-minutes. After a brief rest period, the patient's foot and ankle will be positioned in the splint device to produce dorsiflexion and stretch of the calf muscles and scanning will resume. Due to associated MRI costs, only a subset of patients and controls will be using the MRI. At this time, we anticipate ~25 total subjects will undergo pre/post MRI: 4-6 healthy/placebo; 4-6 healthy/creatine; 6-8 PAD/placebo; 6-8 PAD/creatine. Subjects who undergo MRI will be selected in

PROTOCOL TITLE: Creatine supplementation and muscle stretching in peripheral artery disease patients

the order they present and are eligible to receive an MRI (based on MRI exclusion criteria)

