To reduce the risk of skin irritation associated with the Fitbit, all subjects will be instructed to keep the device clean, dry, and to not wear the device too tightly. If skin irritation occurs and does not resolve within 3 days, subjects will be instructed to discontinue use of the device. If any soreness, tingling, numbness, burning, or stiffness in the hands occurs in the hands or wrists, subjects will be instructed to discontinue use of the device immediately. To reduce risk of the above, subjects will be given the following instructions:

1. Do not attempt to replace the battery, open the enclosure or disassemble your Fitbit product.
2. Do not use your Fitbit product if the display is cracked.
3. Do not expose your Fitbit product to extremely high or low temperatures.
4. Do not use your Fitbit product in a sauna or steam room.

PROTOCOL TITLE: Creatine supplementation and muscle stretching in peripheral artery disease patients

5. Do not use abrasive cleaners to clean your Fitbit product.
6. Remove your Fitbit product immediately if it feels warm or hot.
7. Charge the battery with the charging cable provided. Do not use other cables.
8. Do not wear your Fitbit product while charging it.
9. Do not charge your Fitbit product while it is wet.

Creatine monohydrate will be used in the current investigation. The purpose of using creatine is to create a favorable metabolic environment to improve patients' ability to walk.

- The use of creatine monohydrate in this investigation has been approved by the FDA.

The source records that will be used to collect data about subjects are attached to the IRB submission and will be kept in a locked cabinet in a locked office.

6.4 All data will be collected by trained members of the study team (NIRS, MRI, blood pressure, heart rate, anthropometry, Fitbit, and cardiovascular (i.e., six-minute walk test) variables.

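### No masking of visit or arm is stated for whoever derives the NIRS and MRI values; de-identification under a subject code does not hide pre from post

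*Protocol*

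**What the plan says.** Post-processing is covered in the protocol's confidentiality text. Section 19.1 states: "All data will be deidentified when post processing". Section 17.2 states: "All data, whether generated in the laboratory or in post-processing will be identified with an identification code unique to the subject". Section 15.1 repeats the study-ID rule for questionnaires and imaging, as protection against a breach of confidentiality.

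Two limits on access are given. In 17.2: "The master identification code list will be kept under lock and key access limited to the P.I. and necessary members of the study team". In 19.3, lab help outside the PI and research team is denied "any information to link the data back to the subject".

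On blinding, 6.2 says only: "The current investigation is a randomized single-blind study design". The blinded party is not named. On collection, 6.4 says: "All data will be collected by trained members of the study team".

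On the signals, 6.2 (C4) says: "NIRS measurements will be made continuously during the entirety of the experimental protocol". The cuff is inflated for 5 minutes and released at minute 5, and about 5 minutes of rest follow. The C8 heel raise lasts 1 minute. Under C5.A, muscle blood flow and metabolic kinetics "will be measured in the 3T MRI system (Visit 2 and Visit 3; limited subjects").

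The SAP names microvascular function first in its primary goal and bases its 9 per group on reperfusion variables. It analyses change by group-by-time repeated measures ANOVA. If creatine and placebo do not differ, it pools the arms and tests pre against post with paired t-tests.

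**The concern.** A subject code hides a name. It does not hide which of a subject's two recordings came before the intervention. The paired analysis needs that information at some stage, and the documents do not say that it is withheld until the values have been derived.

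The step leaves some room for judgement. A continuous trace has to be reduced to a number, and neither document says which baseline segment is used or which metric is derived from it. The protocol also states a directional hypothesis (2.2): stretching is expected to improve NIRS oxygenation and MR leg blood flow. A reader who knows the visit could, without intending to, treat post traces slightly differently from pre traces.

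Such a difference would be systematic, so averaging over subjects does not remove it. The SAP's 2-SD outlier rule does not remove it either, because a shift common to all post traces moves the mean change with it. In the pooled paired test it would be read as improvement. A reading difference between arms would enter the group-by-time interaction in the same way.

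Naming who is blinded to product would not settle this, because in the pooled test the whole contrast is visit.

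**Working it through.** **Document check.** The plan gives no figure to reproduce, so the first step is to ask what each stated safeguard hides from the person deriving values.

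| Safeguard | Hides name | Hides visit | Hides arm |
|---|---|---|---|
| De-identification at post-processing (19.1) | yes | not stated | not stated |
| Code unique to the subject (17.2) | yes | no; it is one code per subject, not per visit | only from someone without the allocation |
| Restricted master code list (17.2) | yes | no | indirectly at most |
| No linking information for other lab help (19.3) | yes | no | indirectly; the PI and research team are exempt |
| Single-blind design (1.0, 6.2) | – | no | blinded party not named; the placebo suggests the participant |
| SOPs for calibration and data collection (17.3) | – | not mentioned | not mentioned |

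No row provides masking of visit. Masking of arm is possible for some staff but is not stated for whoever derives the values.

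**Room for judgement.** Occlusion, release and recovery in C4 and the heel raise in C8 follow timed events, so those periods are largely fixed. The baseline segment and the derived metric are not specified.

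**Sensitivity of the tests (illustration only).** The shift sizes are assumptions, since the documents give none. The true effect is set to zero and each test is two-sided at 0.05.

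*Pooled paired t-test.* n = 9 + 9 = 18 (SAP sample size), df = 17, critical t = 2.110. With a consistent reading shift b in SDs of the change, the noncentrality is b × √18 = 4.243b.

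- b = 0.05: 0.212, rejection 5.5%
- b = 0.10: 0.424, rejection 6.9%
- b = 0.25: 1.061, rejection 17.0%
- b = 0.50: 2.121, rejection 51.6%

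*Creatine against placebo.* With two groups and two times, the interaction is equivalent to a two-sample t-test on the changes: 9 v 9, df = 16, critical t = 2.120, noncentrality b × √(9/2) = 2.121b.

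- b = 0.10: 0.212, rejection 5.5%
- b = 0.25: 0.530, rejection 7.9%
- b = 0.50: 1.061, rejection 17.0%

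At the same shift in SD units, the pooled pre/post test is the more exposed of the two.

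**The case against.** The strongest reply is that silence is not disclosure. A reader might infer that arm and visit are openly visible to whoever processes the files, or that the subject code conceals nothing. The documents support neither. They do not say that the labels are visible. The code list is restricted, and a processor holding only a study ID would need the allocation list to know the arm. Section 6.4 says who collects the data; no passage says that the same people derive the values. This stands, and it makes the arm part of the point conditional.

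A reader might also infer that every analysis window is chosen freely. That goes too far, since the cuff and heel-raise timings are fixed. What remains open is the baseline segment and the derived metric.

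The size is hypothetical. About 52% requires a consistent half-SD shift, for which the documents offer no basis on a timed, instrument-recorded signal; at 0.05 SD the pooled rate is 5.5%. The pooled test is also conditional on finding no difference between creatine and placebo, and the study calls itself a pilot. The SOPs cited in 17.3 cannot be seen here, and fully automatic extraction would make the shift zero.

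None of this supplies masking of visit. The stated safeguards still leave that open, and the fallback analysis rests on it.

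**Conclusion.** The point holds in this form: neither document states masking of visit or arm for the person who derives NIRS and MRI values, and de-identification under a subject code does not provide it. Visit is the stronger part. The arm part depends on who can see the allocation, which is not stated.

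The illustrative size is a false-positive rate of about 7% or 17%, against a nominal 5%, for a consistent pre/post shift of 0.10 or 0.25 SD of the change. This assumes 18 pooled patients, no true effect and shift sizes that the documents do not supply. It measures how sensitive the test is. It does not support an inference that readings were biased or that any result is wrong.

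The change is worth making because it protects the outcome on which the sample size rests, at little cost. If masking was in fact done, or extraction was fully automatic, saying so resolves the point.

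**What to change.** Keep the de-identification sentence in 19.1, which is a privacy commitment. Add to 17.2 and to the SAP:

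1. Before extraction, a script or an existing team member who does not extract replaces the subject code, visit label and acquisition date on every NIRS and MRI file with a random file number. The date must go too, because it can reveal pre and post.
2. Values are derived by a fixed extraction rule, which names the baseline segment and the metric, without knowledge of visit or arm.
3. The values are locked, and only then is the key merged with the study database.

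The SAP is written in the past tense, so extraction may already have been done. If it was done unmasked and the raw recordings are retained (the documents do not say so explicitly), re-derive the values once in this way and report any difference. This is preferably done by an existing team member who did not make the first extraction, because someone who has already seen the traces is not cleanly masked.

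The cost is a short addition to each document, a file-renaming step and possibly one re-read. No patients or visits are added.
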